The research involves behavioral interventions in conjunction with the collection of information from an **adult subject** through verbal or written responses (including data entry) or audiovisual recording if the subject prospectively agrees to the intervention and information collection

The behavioral interventions are brief in duration, harmless, painless, not physically invasive, not likely to have a significant adverse lasting impact on the subjects, and the investigator has no reason to think the subjects will find the interventions offensive or embarrassing.

Provided all such criteria are met, examples of such benign behavioral interventions would include having the subjects play an online game, having them solve puzzles under various noise conditions, or having them decide how to allocate a nominal amount of received cash between themselves and someone else.

² Subpart D applicable only when involving educational tests or the observation of public behavior when the investigator(s) do NOT participate in the activities being observed.

One of the following criteria must be met:

3iA) The information obtained is recorded by the investigator in such a manner that the identity of the human subjects **CANNOT** readily be ascertained, directly or through identifiers linked to the subjects

OR

3iB) Any disclosure of the human subjects' responses outside the research would **NOT** reasonably* place the subjects at risk of criminal or civil liability or be damaging to the subjects' financial standing, employability, educational advancement, or reputation

**Reasonably defined as with fair and sound judgment; a standard used by an ordinary, rational person under similar circumstances.*

SECTION 1: STUDY INFORMATION

1. Study Title:

HOPE COVID-19 Vaccine Opinion Study

2. Identify the funding source. *Check all that apply:*

Grant/Subaward **OR** Contract/Subcontract
(provide details below)

Prime Awardee(s): [name]

Sponsor Name(s): NIAID

SPA Proposal or Award #(s): 5R01AI132030-05

Check here to confirm a copy of the human subjects portion of the grant is available and kept on file

Department or campus funds (includes department support, unrestricted funds, start-up funds, personal funds, campus program awards, etc.)

Non-cash support from manufacturer/sponsor (e.g., free drug, device, research materials)

Subject/subject's insurance/third party payer

Student project that will incur no costs.

SECTION 2: STUDY TEAM

1. Complete the table below.

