 CR  RP	[name], MSc Type Here	 Faculty  Staff  Grad Student  Undergrad  Other UCI: Type Here	 N/A  Yes  No	 N/A  Yes  No	 N/A  Yes  No	 N/A  Yes  No	 N/A  Yes  No
 CR  RP	[name] Postdoc	 Faculty  Staff  Grad Student  Undergrad  Other UCI: Postdoc	 N/A  Yes  No	 N/A  Yes  No	 N/A  Yes  No	 N/A  Yes  No	 N/A  Yes  No
To add more study team members, click into this space, then click the new + button on the right 							

5. If applicable, specify which members of the above study team will be responsible for interacting with non-English speaking participants.
 
NA: English speaking participants only
							

SECTION 3: WHAT IS YOUR RESEARCH QUESTION?

1. State the hypothesis or primary objective of the research. Include a rationale for conducting the study. *[Maximum length = 250 WORDS]*

This study seeks to utilize our previously tested Harnessing Online Peer Education (HOPE) online community intervention to connect peer leaders with healthcare personnel and frontline essential workers choosing not to receive the COVID-19 vaccine. Over the 4-week intervention we aim to teach participants about the risks of COVID-19 and the benefits of the COVID-19 vaccine.

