Those who do not qualify to participate in the study will see a web page that thanks them for their interest and tells them that they are not qualified to participate at this time and that their data will not be used and will be destroyed to protect their confidentiality. Those who are unqualified will not be able to access the Informed Consent Information Sheet. If eligible, potential participants will be sent a brief description of the study and the Informed Consent Information Sheet. If they would like to participate in the study they will be asked to continue with the consent process. By clicking continue, they will have implied consent to the study and be routed to a webpage where they can provide an email address and phone number for future contact, as well as begin the baseline survey. After survey completion, they will be instructed to friend request our HOPE Study Facebook profile or be provided a link to join the group.

After 1) consenting to the study (by clicking continue), 2) friending us on Facebook, 3) completing a baseline survey, and 4) joining our private Facebook group (they will be randomly assigned to a group and group request will be sent to them), participants will be officially enrolled in the study.

If participants have yet to friend us or join our private group, we will email them a reminder and/or call them every 24 hours until the invitation is accepted.

In the event that a participant has trouble friending us on Facebook, participants may alternatively be sent a link to join the Facebook group.

If the baseline survey is not completed after 48 hours, we will attempt to reach the participant by phone every day until we successfully make contact. We may call them multiple times per day up to a maximum of 3 attempts.

Peer Leader Recruitment:

Up to 30 peer leaders will be recruited using online advertisements as above, as well as by direct message of healthcare personnel or frontline essential worker that has shared a picture of their vaccine card or vaccination sticker online, for example on Reddit. Advertisements will be designed to recruit people who are social online (e.g., chat frequently online, create TikTok videos, etc.) and report having received the COVID-19 vaccine. Potential peer leaders who click on the ads will be routed to a website/survey (such as Qualtrics) where they are screened online for eligibility with our questionnaire.

Inclusion criteria:

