Participants will be randomly assigned to an intervention or control group (each group will have approximately 30 participants and approximately 6 peer leaders (depending on recruitment and people that may drop out)). There will be 5 control groups and 5 intervention groups total. Those in the control group will be assigned to a private and hidden Facebook group and told they can interact with each other as they wish. Those in the intervention group will be assigned to peer leaders, also in a private and hidden Facebook group, with each participant assigned to have approximately 2-3 peer leaders. Facebook groups will also become hidden once all group participants are in the group. The intervention will take place over 4 weeks, with a possible week 0 before the study officially starts to allow peer leaders and participants to become accustomed to each other and the Facebook group features. Each week of the intervention, peer leaders will reach out to participants by posting on the online group forum, either text, images, or videos and sending direct messages to participants, attempting to promote COVID-19 vaccination through comforting and educational information/content of their choice. Every 2 weeks through the end of the study, participants in both conditions will be invited to email us to receive information about and receive related resources for COVID-19 vaccination, such as pamphlet on vaccination information. At the end of the 4-week intervention, participants will complete the final survey. Participants will be paid \$15 in Amazon gift cards for the baseline survey, \$20 in Amazon gift cards for the final survey, and \$15 in Amazon gift cards for providing proof of vaccination if applicable. Participants should expect about 4-6 weeks after completing respective tasks before receiving compensation. Participants will be contacted by phone and/or email to remind them to complete surveys as discussed above for the baseline survey.

All analyses will be conducted in R (version 4.1.2) We will assess the effect of the HOPE intervention on the primary outcome (whether a participant requested vaccine information during the study), and the secondary outcome (whether a participant got the vaccine during the study). We will adjust for race (dichotomized by Caucasian vs other), age (above vs. below 40), sex from birth, education (bachelor or below vs. grad school or above), and ethnicity (Latino vs. other).

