Check here to confirm Letter(s) of Permission has been / will be obtained for non-UCI private locations and kept on file.

3. List the data collection procedures in chronological order using the table format below.

Procedure and/or the Data Collection Instrument	Is the Procedure/Instrument already being completed as part of a program evaluation or an educational activity?	Is the Procedure/Instrument a standardized measure?	List the frequency and the time required for participants to complete the Procedure/Instrument	Describe the setting where data collection will take place	Confidentiality: Are participant identifiers (IDs) recorded during data collection?
EXAMPLE: ABC Satisfaction Survey via Amazon Turk	 N/A  Yes  No	 N/A  Yes  No	Survey will be completed 3x during the academic year. Takes no more than 20 mins. to complete	Amazon Mechanical Turk	 No IDs  Code with link to IDs  Yes IDs
Online Screener	 N/A  Yes  No	 N/A  Yes  No	Takes a couple minutes to complete.	Internet	 No IDs  Code with link to IDs  Yes IDs

Baseline Survey	 N/A  Yes  No	 N/A  Yes  No	Takes 15 minutes to complete	Internet	 No IDs  Code with link to IDs  Yes IDs
4-Week Survey	 N/A  Yes  No	 N/A  Yes  No	Takes 15 minutes to complete	Internet	 No IDs  Code with link to IDs  Yes IDs

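### Both outcomes are adjusted only for five two-level demographics; one baseline willingness-to-vaccinate item should be prespecified as a covariate

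*Combined protocol and SAP*

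**What the plan says.** Section 5 (Methods) names two binary outcomes: the "primary outcome (whether a participant requested vaccine information during the study") and the "secondary outcome (whether a participant got the vaccine during the study"). The adjustment statement follows directly and covers both: "We will adjust for race (dichotomized by Caucasian vs other), age (above vs. below 40), sex from birth", then education (up to bachelor against graduate school) and ethnicity (Latino against other). The primary model is a logistic mixed model or GEE. The secondary model is GEE with exchangeable correlation by Facebook group.

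Section 5 lists the steps that complete enrolment, among them "3) completing a baseline survey, and 4) joining our private Facebook group", with random assignment to a group mentioned at the last step. A second survey comes later: "At the end of the 4-week intervention, participants will complete the final survey". The Section 8 table says of each survey "Takes 15 minutes to complete", and Section 6 pays $15 and $20 for them. No section states what either survey asks or how its answers will be analysed. No stratified randomisation is described.

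**The concern.** Inclusion criterion 7 admits only people who are unvaccinated and have no medical or other barrier to vaccination. Among them, how willing a person already is at baseline is a natural candidate for the strongest predictor of later vaccination, and age, sex, race, ethnicity and education are likely to be weak stand-ins for it. The plan spends five model terms on those stand-ins and none on willingness, although a survey is already administered at the right moment. What is at stake is some power, and protection against a chance difference in willingness between arms that demographic adjustment would not remove.

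**Working it through.** **No planned figure to reproduce.** The documents give no event rates, effect size, power, alpha or intraclass correlation. Every rate below is an assumption.

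**Sample size.** Section 4 gives a maximum of 120 (60 per arm). Section 5 gives 10 groups of about 30, which is 10 × 30 = 300 (150 per arm). The two need reconciling; both are used here.

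**Chance imbalance.** The standardised difference in a baseline score has SD sqrt(2/n) with n per arm.
- At 120 in total: sqrt(2/60) = 0.183, so P(|difference| > 0.2) = 27%.
- At 300 in total: sqrt(2/150) = 0.115, so the same probability is 8%.

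**What imbalance does to the vaccination difference.** Assume 40% of participants are open to vaccination and 60% closed, with 30% and 3% later vaccinated.
- SD of the arm difference in the open fraction: sqrt(2 × 0.4 × 0.6/60) = 0.089.
- Effect on the vaccination difference: 0.089 × (0.30 − 0.03) = 2.4 points per SD. At 150 per arm it is 1.5 points.
- Overall rate: 0.4 × 0.30 + 0.6 × 0.03 = 0.138. Unadjusted SE: sqrt(2 × 0.138 × 0.862/60) = 6.3 points.
- Within-class variance: 0.4 × 0.21 + 0.6 × 0.0291 = 0.1015. SE with willingness imbalance removed: sqrt(2 × 0.1015/60) = 5.8 points.

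The 2.4 points is therefore a component of the 6.3 (5.8² + 2.4² ≈ 6.3²) and not an addition to it.

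**Power.** Logistic regression of vaccination on arm plus five unrelated binary covariates, with and without willingness; two-sided 5% Wald test; n = 120; no clustering. Willingness is an evenly spread 5-point item (SD 1.41) entered linearly. There were 4,000 simulated trials per row, and the Monte Carlo error of each gain is about 0.3 to 0.6 points.

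| Log-odds per point (OR per SD) | 12% vs 25% | 12% vs 30% |
|---|---|---|
| 0.25 (1.4), weak | 44% to 44% | 66% to 66% |
| 0.5 (2.0), moderate | 44% to 47% | 67% to 69% |
| 1.0 (4.1), strong | 43% to 51% | 68% to 77% |

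Other runs, with different rates or a continuous score, fall in a similar range. At n = 120 the gains were 0 to 2 points at an odds ratio of 1.5 per SD, 2 to 3 at 2, and 5 to 6 at 3. Runs at log-odds 1.0 per point gave gains as low as 4 points (45% to 49%). A predictor as strong as 5 per SD gave about 10 to 14 points. At n = 300 and 10% vs 22%, power went from 81% to 84% at 2 per SD.

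**Precision, strong predictor, 12% vs 25%.**
- Median SE of the log-odds ratio: 0.53 without willingness, 0.62 with it. It rises. Power improves because the conditional log-odds ratio is further from zero.
- SD of the risk difference standardised from the same models: about 0.072 to 0.064, a variance ratio of (0.064/0.072)² = 0.79. With a weak or moderate predictor this SD barely changes.

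**Events available.** At 12% vs 25% and 60 per arm, expected vaccinations are 7.2 + 15 = 22.2. Arm, five demographics and willingness make 7 terms, or about 3 events per term, so the order in which covariates are kept matters.

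**The case against.** The strongest reply is that the documents do not show a useful measure being left unused. The title, "HOPE COVID-19 Vaccine Opinion Study", suggests that opinion is surveyed, but only the length, timing and payment of the surveys are stated. A reader might infer that willingness is measured and then discarded. That cannot be established, and if it is not measured the advice is to add a question. This stands, and the fix is worded to cover both cases.

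The gain also depends on prognostic strength, which is unknown. Section 4 describes the participants as people who have refused the vaccine, so the spread of willingness may be narrow and the gain near zero. This stands too.

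Four further inferences are tempting and not supported:
- That the omission biases the result. Under randomisation it does not, on average, and the unadjusted standard error already includes chance imbalance.
- That adjustment narrows the interval for the odds ratio. It does not.
- That type I error under the planned analysis is assured. The roughly 5 to 6% seen with independent logistic regression does not carry over to GEE with 10 groups. Simulated with ordinary sandwich errors at n = 120, that gave about 10 to 15% with or without willingness. The covariate is not the cause, but the power figures above do not describe the planned GEE.
- That the plan is wrong to omit a week-4 attitude outcome because Section 3 says "we aim to teach participants about the risks of COVID-19 and the benefits of the COVID-19 vaccine". Section 3 also presents raising vaccination rates as the goal, and both named outcomes are behavioural. Adding an attitude outcome is a choice of endpoint and affects neither power nor imbalance for the outcomes named.

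**Conclusion.** The point holds as a modest, inexpensive improvement and not as an error that undermines the trial. The adjustment set leaves out the baseline characteristic most plausibly related to vaccination, at a stage where it could be collected at almost no cost. For vaccination at n = 120 the expected gain is about 0 to 2 power points for a weak predictor, 1 to 4 for a moderate one and 4 to 9 for a strong one, with better precision on the risk-difference scale only.

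These figures assume control and intervention rates of roughly 10 to 20% and 25 to 40%, demographics unrelated to outcome, and no clustering. Clustering in 10 groups would lower absolute power but should not reverse the direction of the comparison. For the primary outcome the gain is unquantified: people already decided either way may not ask for information, so a linear relation with willingness is less certain there.

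**What to change.** In the Section 5 analysis paragraph, name one ordinal item on willingness to be vaccinated as a covariate in the models for both outcomes, entered as a linear term. Use an existing baseline survey item if there is one; otherwise add a single question. State that it must be answered before group assignment, since the enrolment list implies that order without saying that assignment waits for the survey. State also that, if events are too few to support all covariates, willingness is kept ahead of the demographics.

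The cost is one more model term, at most one survey question, and an odds ratio that becomes conditional on willingness; reporting a standardised risk difference beside it would show the effect on the scale where precision can improve. Saying what the two surveys measure and how the responses will be analysed would be helpful. A week-4 attitude outcome is optional.

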The intervention effect on the primary outcome will be assessed using logistic mixed effects models or generalized estimating equations.

The intervention effect on the secondary outcome will be assessed using generalized estimating equations with an exchangeable correlation structure ([2]), which accounts for the clustering by Facebook group. Engagement in the study is defined as participants that posted, commented, voted, or reacted to anything within a given week.

SECTION 6: PARTICIPANT COMPENSATION

Will participants be compensated?

IMPORTANT! Compensation should be offered on a prorated basis when the research involves multiple sessions. Additional considerations are required when using lotteries, raffles, and drawings, see UCI [Lottery Guidance](#). For additional information about researcher's/department's responsibilities and current Accounting procedures, see [UCI Policy Sec. 701-03](#).

Participants will not be compensated. ***Skip to SECTION 7.***

Participants will be compensated, ***address the following:***

Amount of Payment: Participants will be compensated \$15 for the baseline survey, \$20 for completing the 4-week survey, and an additional \$15 if they show proof of at least the first dose of vaccination (send us picture of vaccine card). Up to a total of \$50.

Peer Leaders will be compensated \$20 for each week they turn in their complete response sheet on time. Total of \$80 if all response sheets are turned in complete and on time.

Method: Cash Check Extra credit Gift card: [Amazon Gift Card](#) Other: [Type Here](#)

Schedule: After each study visit At the end of study Other : [Type Here](#)

SECTION 7: INFORMED CONSENT PROCESS

1. Identify the specific steps for obtaining consent.

IMPORTANT! For additional information, see [Guidance for Consenting Process](#). Templates are available on the HRP webpage [Application and Forms](#) (see sub-section HRP, Consent Forms).

No consent process will take place (i.e., no contact with participants) ***Skip to SECTION 8.***

Oral / Implied informed consent will be obtained – No signature is required (e.g., completion of a survey electronically)

IMPORTANT!

- Customize the Study Information Sheet template.
- If obtaining consent online, participants should:
 - View the Consent/Study Info Sheet prior to participation
 - Be prompted to verify they meet the eligibility criteria, and
 - Indicate their willingness to participate in the research (e.g., click “Yes”).

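### Neither outcome analysis has a small-sample method for 10 Facebook groups, and the primary model is left open: an uncorrected GEE z test would roughly double a 5% false-positive rate

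*Combined protocol and SAP*

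**What the plan says.** The analysis plan is the last part of the Methods text in Section 5 (Recruitment Methods).

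- **Primary outcome** (request for vaccine information, yes or no): "The intervention effect on the primary outcome will be assessed using logistic mixed effects models or generalized estimating equations". No rule for choosing is given, and no cluster unit, random effect or working correlation is stated for this outcome.
- **Secondary outcome** (vaccination, yes or no): "The intervention effect on the secondary outcome will be assessed using generalized estimating equations with an exchangeable correlation structure", "which accounts for the clustering by Facebook group".
- **Clusters:** "There will be 5 control groups and 5 intervention groups total", and "each group will have approximately 30 participants and approximately 6 peer leaders". Sizes are said to depend on recruitment and dropout.
- **Covariates:** "We will adjust for race (dichotomized by Caucasian vs other), age (above vs. below 40), sex from birth, education" and ethnicity, so five binary adjusters.
- **Software:** R 4.1.2, with no function, standard error type or reference distribution.

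No significance level, ICC, expected outcome rate or power calculation is given. Section 4 (Subject Population) sets a maximum of 120 participants.

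**The concern.** The sandwich variance in GEE is estimated from the spread between clusters. Five clusters per arm make it biased downwards and noisy. Referring the estimate to a normal distribution ignores both faults, so p-values come out too small and intervals too narrow. A mixed model has a related weakness: its between-group variance rests on 10 groups. The gap affects both outcomes, since the secondary GEE has the same 10 groups and no correction either.

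The open choice for the primary outcome is a further gap. A mixed model gives an odds ratio conditional on the group, while GEE gives one averaged over groups. When groups vary these are different quantities, so the plan does not fix what the primary result estimates.

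**Working it through.** **Inputs from the documents.** 5 + 5 = 10 groups, leaving 10 - 2 = 8 between-group degrees of freedom. About 30 participants per group, or 120/10 = 12 if the Section 4 maximum is spread over 10 groups. Binary outcome, five binary covariates. There is no planned error rate or power figure to reproduce.

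**Assumptions.** Two-sided 5%; outcome rate 10%-30%; outcome-scale ICC 0-0.10; ordinary Wald tests against 1.96 unless stated.

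**Step 1: GEE by algebra.** Take K = 5 equal groups per arm and no covariates. The uncorrected sandwich variance of an arm's mean is (K-1)/K = 4/5 of the unbiased between-group value. If group results are roughly normal, rejecting when |z| > 1.96 is the same as rejecting when |T| > 1.96 x sqrt(0.8) = 1.753, with T on 8 df. That has a true size of 11.8%. Even with an unbiased variance, T on 8 df judged at 1.96 has size 8.6%; the correct critical value is 2.306. The Kauermann-Carroll correction multiplies the variance by 5/4 here and, with t on 8 df, restores 5% under this approximation.

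**Step 2: null simulation, 5 v 5 equal groups of 12 or 30, beta-binomial group rates.**

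| Test | No covariates, ICC 0-0.05 | Five covariates, ICC 0 and 0.05 |
|---|---|---|
| GEE, uncorrected, z | 9.5%-13.2% | 11.2%-14.3% |
| Mixed model, z | 2.2%-10.6% | 4.1%-11.5% |
| GEE, Kauermann-Carroll, t(8) | 2.4%-5.8% | 4.8%-5.7% |
| Mixed model, t(8) | 0.6%-6.3% | 1.5%-6.8% |

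The first column covers 18 scenarios (rates 10%, 15%, 30%; 4,000 trials each), the second 8 (rates 15%, 30%; 2,000 trials each). Monte Carlo standard errors are about 0.2-0.8 points. Without covariates the mixed-model z test gave 2.2%-4.8% at ICC 0 and 5.4%-10.6% at ICC 0.05.

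**Step 3: wider conditions.** Extending the no-covariate GEE check to ICC 0.10 gave 9.4%-13.9% uncorrected and 2.4%-5.8% corrected. A separately coded run with five covariates gave uncorrected GEE 10.8%-12.3% at ICC 0. A smaller run with logit-normal group effects (600 trials per scenario) spread further: 7.4%-15.0% for GEE z and 2.8%-11.3% for mixed z. One mixed-model scenario at ICC 0.10 (30 per group, rate 10%, five covariates) gave 19.5% with z and 13.6% with t(8). Repeating it without covariates on a finer integration grid brought both rates well down, so they are not relied on here.

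**Step 4: cost of the open choice.** Under the null the two uncorrected tests disagree in 2.2%-7.8% of trials (2.3%-9.0% with covariates). Declaring success if either is significant adds 0.1-0.9 points to the GEE rate (0.2-1.0 with covariates). That bound is for ICC up to 0.05: in the logit-normal run, one scenario with ICC about 0.07 added 15.2 - 13.3 = 1.9 points.

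**Step 5: unequal groups.** With 4, 8, 12, 16 and 20 participants per group in each arm (assumed; no covariates), corrected GEE on t(8) rejected 3.8%-9.0% when the working correlation could go well below zero, and 3.1%-5.7% when held at zero or above. Mild imbalance gave 2.8%-5.9%.

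**The case against.** **The plan never says z test.** This stands. A reader might infer that a faulty test has been chosen, but the text names no variance estimator, test or significance level. The secondary-outcome sentence also cites a reference that is not supplied, so what lies behind it cannot be checked. The fault is an omission, and the 9%-14% figure is conditional on the uncorrected test.

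**Participants are individually randomised, so group correlation may be small.** This is fair for the mixed model. A reader might infer that both permitted models are inflated, but at ICC 0 the mixed-model z test is not. It does not rescue uncorrected GEE, which is too liberal even at ICC 0.

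**The open choice invites picking the significant result.** A reader might take this as the main harm. The documents do not say that both models will be run, and the added error is about 1 point at most for ICC up to 0.05.

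**The cluster unit is easy to infer.** True: the secondary-outcome sentence names Facebook group. That settles neither the primary model nor the reference distribution.

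**The remedy is one of several.** Also true. A t test on the ten group proportions rejected 3.1%-5.7% under the null and is simpler, though unadjusted. Mancl-DeRouen correction with t(8) gave 1.0%-3.6%, which is controlled but conservative.

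**Conclusion.** The point holds as an omission that affects both outcomes. With 10 groups, following the plan with an ordinary uncorrected GEE z test would give about 9%-14% false positives where 5% is intended. Rates, ICC, test and significance level are all assumptions here. The GEE result does not hinge on the ICC: the algebra gives 11.8% whatever its value, if group results are roughly normal. The mixed model's error does depend on the ICC, which the plan does not state, so its error rate cannot be known in advance. The open model choice is a smaller problem for error control, but it leaves the estimand unsettled.

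A reader might combine the maximum of 120 with about 30 per group and conclude that there are only 4 groups, which would make matters worse. The documents do not support that, because Section 5 states 5 and 5. They do contradict themselves on size: 10 x 30 is about 300, not 120.

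**What to change.** Before outcome data are examined, add to the analysis text:

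1. **One primary model.** For example, logit GEE with exchangeable correlation, Facebook group as cluster and the five stated covariates, with the marginal odds ratio named as the estimand. State the significance level and sidedness.
2. **A small-sample method for both outcomes.** For example, a Kauermann-Carroll corrected sandwich variance with a t reference on groups minus 2 degrees of freedom (8 for 10 groups). Hold the working correlation at zero or above, since group sizes are only approximate.
3. **The mixed model as a labelled sensitivity analysis only.** Use a Facebook-group random intercept and t on groups minus 2, with a note that this test can still be liberal at higher ICC. It cannot replace the primary result.
4. **Separately, reconcile** 10 groups of about 30 in Section 5 with the maximum of 120 in Section 4, because the number of groups sets the degrees of freedom.

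The cost is a few sentences and no new data. Intervals widen, and the test is conservative at low request rates (2.4%-2.7% at 12 per group and a 10% rate). Under assumed effects of 15% v 30% or 30% v 50%, corrected GEE rejects 8-21 percentage points less often than uncorrected GEE z and 6-19 points less often than mixed-model z. Part of that gap is the inflated error of the uncorrected tests.

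### GEE on ten Facebook groups with no small-sample correction: in its ordinary form, a nominal 5% test has a false-positive rate of about 11-14%

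*Combined protocol and SAP*

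**What the plan says.** All of this is in the Methods text of Section 5 (Recruitment Methods) of the combined protocol and SAP.

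- **Clusters.** "There will be 5 control groups and 5 intervention groups total". Group size is approximate and expected to vary: "each group will have approximately 30 participants and approximately 6 peer leaders (depending on recruitment and people that may drop out".
- **Allocation.** "Participants will be randomly assigned to an intervention or control group".
- **Secondary outcome.** It is binary: "the secondary outcome (whether a participant got the vaccine during the study". It is analysed by "generalized estimating equations with an exchangeable correlation structure ([2]), which accounts for the clustering by Facebook group".
- **Primary outcome** (a request for vaccine information). "The intervention effect on the primary outcome will be assessed using logistic mixed effects models or generalized estimating equations". The choice is left open, and this sentence does not say what the clusters would be.
- **Covariates.** "We will adjust for race (dichotomized by Caucasian vs other), age (above vs. below 40), sex from birth, education", and ethnicity: five binary variables in all.

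The software is R 4.1.2, with no package or option named. The available text gives no variance estimator, degrees of freedom, bias correction, permutation test or cluster-level analysis. It also gives no alpha, expected event rate, intracluster correlation (ICC) or sample-size calculation.

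**The concern.** The sandwich variance used with GEE is justified as the number of clusters grows. Here that number is ten, however many people each group holds. Two errors then act in the same direction: the uncorrected sandwich variance is biased downward, and comparing the Wald ratio with a normal distribution ignores how poorly ten clusters estimate that variance. Naming an exchangeable working correlation cures neither.

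Vaccination is the outcome closest to the study's rationale in Section 3. Under the ordinary form, a claim that HOPE raises vaccination could be made at more than twice a 5% error rate. The same applies to information requests if GEE clustered by Facebook group is chosen for the primary outcome. Because the plan leaves the form open, the choice could also be made after the results are known, and the permitted versions give materially different p-values.

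**Working it through.** The plan has no figure of its own to reproduce.

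**Inputs from the plan.** K = 10 groups, 5 per arm; about 30 per group (Section 5), or 120 / 10 = 12 per group from the maximum enrolment in Section 4; binary outcome; five binary covariates. The conflict between 120 and 10 x 30 = 300 is a separate matter, so both sizes were run.

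**Assumed.** Two-sided 5%; event rate 15% or 30%; ICC 0 or 0.05.

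**Analytic check (equal groups, arm only).** The uncorrected sandwich variance is about (K - 2)/K = 8/10 of the unbiased between-group variance. The true size is therefore 2 x P(t8 > c x sqrt(0.8)), where c is the critical value. Kauermann-Carroll multiplies the standard error by sqrt(1.25) and Mancl-DeRouen by 1.25. The t(8) critical value is 2.306.

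- Uncorrected, z: 1.96 x 0.894 = 1.753, size **11.8%**; coverage 100 - 11.8 = 88.2%
- Uncorrected, t(8): 2.306 x 0.894 = 2.063, size 7.3%
- Kauermann-Carroll, t(8): 2.306 x 0.894 x 1.118 = 2.306, size 5.0%
- Mancl-DeRouen, t(8): 2.306 x 0.894 x 1.25 = 2.578, size 3.3%

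**Simulation under no effect.** Exchangeable logit GEE with beta-distributed group rates, 2,000 trials per cell. Unequal groups ranged from 6 to 18 (total 120) or 15 to 45 (total 300). The Monte Carlo standard error is about 0.7 points near 12% and 0.5 near 5%. At most 48 of 2,000 fits (2.4%) in any cell failed to converge and were dropped. Ranges across cells with five inert covariates in the GEE:

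| Test | Equal groups | Unequal groups |
|---|---|---|
| Uncorrected, z | 11.1%-13.6% | 11.6%-15.8% |
| Uncorrected, t(8) | 6.8%-8.8% | 8.2%-11.3% |
| Kauermann-Carroll, t(8) | 4.5%-5.3% | 5.3%-7.2% |
| Mancl-DeRouen, t(8) | 2.0%-3.2% | 2.6%-3.6% |
| t-test on 10 group proportions | 4.6%-5.6% | 4.0%-5.5% |

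With equal groups the uncorrected z-test averaged 12.6% with covariates and 11.6% with arm only. The covariates add about 1 point; the cluster count does the rest.

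**Wider sensitivity run (equal groups).** Event rates 10%-50%, ICC 0-0.10, 64 scenarios of 4,000 trials. Uncorrected z gave 10.7%-14.3% in all 32 covariate-adjusted scenarios. Without covariates most scenarios gave 10.6%-12.5%. The exceptions were 8.7%-9.9% at a 10% event rate with 12 per group, and 14.5% at a 10% rate with 30 per group and ICC 0.10. The inflation is present at ICC = 0 and hardly depends on whether groups hold 12 or 30. In the sparsest adjusted setting up to 520 of 4,000 fits (13%) failed or were degenerate and were excluded. This run did not include Kauermann-Carroll.

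**The case against.** **The plan is silent rather than wrong.** It never names an uncorrected sandwich or a z-test, so every figure is conditional on that form being used. This is true, and the conclusion is worded that way. But the form is permitted, and it is the ordinary one.

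**Citation [2] might specify a correction.** Its content cannot be checked from the available text. As placed, it supports GEE and the exchangeable structure, and the sentence specifies nothing further. The caveat stands; it does not remove the need to state the method.

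**The size depends on assumptions.** Alpha, event rate and ICC are all assumed, and a rare outcome in an unadjusted model with 12 per group gives only about 9%. The plan describes an adjusted model, for which no scenario fell below 10.7%.

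**The reach is limited.** The firm commitment to GEE covers only the secondary outcome. That stands. These calculations also say nothing about how a logistic mixed model would behave with ten groups.

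**Kauermann-Carroll is not the only adequate choice.** Mancl-DeRouen with z gave mostly 4.5%-6.5% (range 2.9%-8.2%) in the wider run, and the group-proportion t-test held its size better than Kauermann-Carroll when groups were unequal. This has force. Kauermann-Carroll with t(8) keeps the planned adjusted model and comes close to 5%, but it needs the cluster-level test beside it. Fixing one adequate method before the data are seen matters more than which one it is.

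**Conclusion.** The concern holds and should be fixed. If the vaccination GEE is run with an uncorrected sandwich standard error and a z-test, a nominal two-sided 5% test has a true size of about 11-14% with equal groups, and up to about 16% with the unequal sizes tried. The result follows mainly from having ten clusters and is stable across the assumed event rates, ICCs and group sizes, apart from the unadjusted rare-outcome case. It extends to the primary outcome only if GEE clustered by Facebook group is chosen there. A t(8) reference without a variance correction does not cure it.

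**What to change.** Add to the analysis text in Section 5:

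> Every GEE test and confidence interval for the intervention effect will use the Kauermann-Carroll bias-corrected sandwich variance and a t distribution with degrees of freedom equal to the number of groups minus 2 (8 as planned). For both outcomes, whichever model is used for the primary, a t-test or permutation test on the group proportions will be reported as a robustness check.

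Before data are seen, say which of the two cluster-level tests will be used. A 5-versus-5 permutation test has 252 allocations, so its smallest two-sided p-value is 2/252 = 0.008, which is usable at 5%. Tying the degrees of freedom to the realised number of groups keeps the rule valid if fewer than ten are formed.

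**Cost.** Two sentences and a few lines of R, with no change to design or data collection. Intervals widen and power falls. For equal groups without covariates the width ratio to uncorrected z is 1.177 (t(8) for z) x 1.118 (variance correction) = 1.32. With the five covariates the median simulated increase is 32%-35%, or 33%-37% with unequal groups. Mancl-DeRouen with t(8) would cost more: 47% unadjusted and 48%-56% adjusted.
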